7.2. Safety Analyses

7.2.1. Overview of Planned Analyses

The safety analyses will be based on the “Safety” population, unless otherwise specified.

Table 4 provides an overview of the planned analyses, with further details of data displays being presented in Appendix 11: List of Data Displays.

Table 4 Overview of Planned Safety Analyses

Endpoint / Parameter/ Display Type	Absolute		
	Summary		Individual
	T	F	L
Adverse Events (AEs)			
All AEs by SOC	Y		Y
Serious AEs by SOC	Y		Y
AEs Leading to Withdrawal from Study by SOC and PT	Y		Y
AEs based on Intensity	Y		Y
Relationship Between AE SOCs, PT & Verbatim Text			Y
Death			
Number of deaths	Y		Y

NOTES:

- T = Table, F = Figures, L = Listings, Y = Yes display generated, SOC = System Organ Class, PT = Preferred Term.
- Summary = Represents TF related to any summaries (i.e. descriptive statistics) of the observed raw data.
- Individual = Represents FL related to any displays of individual subject observed raw data.

9.1. Appendix 1: Time & Events

9.1.1. Protocol Defined Time & Events

Table 1 Time and Events – Pilot Phase

Procedures	Clinic Visit	Home Monitoring (~ 3 days)	Telephone Contact ^a (TC)	Repeat Clinic Visit ^b	Home Monitoring ^b (~ 3 days)	Telephone Contact ^{a,b}	EWD
	Screening Day 0						
Informed consent	X						
Eligibility criteria	X						
Demography	X						
Medical and ALS history	X						
Brief neurological exam	X			X			
AEs/SAEs	X		X	X		X	X
Sensor placement	X	X		X	X		
Reference tasks	X			X			
Subject completes diary		X			X		
Site obtains diary information			X			X	X
Device impact questionnaire			X			X	X

- a. Telephone contact to follow the 3-day home monitoring period to ensure the subject has completed the home monitoring period, diary, and to assess AEs, as appropriate. The expectation is that this call would occur on the first weekday following the home monitoring period.
- b. May be repeated as necessary

Table 2 Time and Events – Core Study Phase

Study Day/Week ^a	Screen/Baseline Day 1/Week 0	Weeks 0, 4, 8	Week 12	Weeks 12, 16, 20	Week 24	Weeks 24, 28, 32	Week 36	Weeks 36, 40, 44, 48 ^c	Week 48 or EWD
	Clinic Visit 1 ^b	Home Monitoring (~3 days)	Clinic Visit 2	Home Monitoring (~3 days)	Clinic Visit 3	Home Monitoring (~3 days)	Clinic Visit 4	Home Monitoring (~3 days)	Clinic Visit 5
Procedures									
Informed consent	X ^d								
Eligibility criteria	X ^d								
Demography	X ^d								
Medical and ALS history	X ^d								
Neurological exam	X								
Smoking details	X		X		X		X		X
Brief neurological exam			X		X		X		X
AEs/SAEs ^e	X	X	X	X	X	X	X	X	X
Concomitant medications ^e	X	X	X	X	X	X	X	X	X
ALSFRS-R ^e	X	X	X	X	X	X	X	X	X
FVC	X		X		X		X		X
Speech assessment	X		X		X		X		X
Sensor placement	X	X	X	X	X	X	X	X	X
Reference tasks	X		X		X		X		X
Device impact questionnaire			X		X		X		X
Subject completes diary		X		X		X		X	
Site obtains diary information ^f		X	X	X	X	X	X	X	X
Follow-up Telephone Contact ^g		X		X		X		X	

- a. Clinic visits and home monitoring periods should be conducted within ± 7 days of the scheduled visit/home period and should be scheduled according to the Baseline Visit.
- b. Subjects transitioning from the Pilot Phase do not need to perform these procedures.
- c. The Week 48 home monitoring period will occur the three days prior to the Week 48 in-clinic visit (Visit 5).
- d. Assessed in clinic at Weeks 0, 12, 24, 36, and 48 and by telephone at Weeks 0, 4, 8, 12, 16, 20, 24, 28, 32, 36, 40, and 44.
- e. Assessed in clinic at Weeks 0, 12, 24, 36, and 48 and by telephone at Weeks 4, 8, 16, 20, 28, 32, 40, and 44.
- f. Diary information should be obtained by telephone at Weeks 0, 4, 8, 12, 16, 20, 24, 28, 32, 36, 40, and 44.
- g. Telephone contact to follow each 3-day home monitoring period. The expectation is that this call would occur on the first weekday following the home monitoring period.

9.2. Appendix 2: Study States and Phases

9.2.1. Treatment States for AE Data

Treatment State	Definition
Onset Time Since 1 st (Days)	If Start Date of wearing the device or date of first protocol specified procedure > AE Onset Date Onset Date = AE Onset Date - Start Date of wearing the device If Start Date of wearing the device or date of first protocol specified procedure ≤ AE Onset Date Onset Date = AE Onset Date - Start Date of wearing the device + 1 Missing otherwise.
Duration (Days)	AE Resolution Date – AE Onset Date + 1
Study-related	If relationship to study participation marked 'YES' on [Inform/CRF OR value is missing].

Note: wearing the device refers to either the at home monitoring, or the use of the device to carry out the in clinic set reference tasks.

9.3. Appendix 3: Data Display Standards & Handling Conventions

9.3.1. Study Treatment & Sub-group Display Descriptors

Treatment Group Descriptions	
	Data Displays for Reporting
Code	Description
A	Mega Faros Device + Fast fix

9.3.2. Baseline Definition & Derivations

9.3.2.1. Baseline Definitions

For all endpoints the baseline value will be the latest assessment prior to or at the baseline visit (Visitnum=10 or 90), with the following exceptions which may use the TC at week 0 (Visitnum=100) if available:

- Actigraphy endpoints
- HRV endpoints
- Speech endpoints
- ALSFRS-R
- FVC

For all endpoints this will be referred to as Baseline, Week 0.

9.3.2.2. Derivations and Handling of Missing Baseline Data

Definition	Reporting Details
Change from Baseline	= Post-Baseline Visit Value – Baseline
% Change from Baseline	= 100 x [(Post-Baseline Visit Value – Baseline) / Baseline]

NOTES:

- Unless otherwise specified, the baseline definitions specified in Section 9.3.2.1 Baseline Definitions will be used for derivations for endpoints / parameters and indicated on summaries and listings.
- Unless otherwise stated, if baseline data is missing no derivation will be performed and will be set to missing.

9.3.3. Reporting Process & Standards

Reporting Process	
Software	

 • The currently supported versions of SAS software will be used. 	
Reporting Area	
HARP Server	:UK1salx00175
HARP Area	:175\gsk1223249\mid201283
QC Spreadsheet	: Mc Laren-QC Sheet

Reporting Process	
Analysis Datasets	

 Analysis datasets will be created according to IDSL standards. 	
Generation of RTF Files	

 RTF files will be generated for all the summary tables. 	

Reporting Standards	
General	

 The current GSK Integrated Data Standards Library (IDSL) will be applied for reporting, unless otherwise stated: 
 4.03 to 4.23: General Principles 5.01 to 5.08: Principles Related to Data Listings 6.01 to 6.11: Principles Related to Summary Tables 7.01 to 7.13: Principles Related to Graphics 	
Formats	

 GSK IDSL Statistical Principles (5.03 & 6.06.3) for decimal places (DP's) will be adopted for reporting of data based on the raw data collected. Numeric data will be reported at the precision collected on the eCRF. The reported precision from non eCRF sources will follow the IDSL statistical principles but may be adjusted to a clinically interpretable number of DP's. 	
Unscheduled Visits	

 Unscheduled visits will not be included in summary tables. 
 If unscheduled visits are included, provide details of how summaries will be displayed (i.e. unscheduled visits will be slotted to closest planned visit). Unscheduled visits will not be included in figures. All unscheduled visits will be included in listings. 	
Descriptive Summary Statistics	
Continuous Data	Refer to IDSL Statistical Principle 6.06.1
Categorical Data	N, n, frequency, %
Graphical Displays	

 Refer to IDSL Statistical Principals 7.01 to 7.13. 	

9.4. Appendix 4: Derived and Transformed Data

9.4.1. General

Multiple Measurements at One Time Point

 For the ALSFRS-R, if the closest assessment is not evaluable, the other assessment would be used.
Study Day

 Calculated as the number of days from baseline visit (visitnum=10 or 90) 
 Ref Date = Missing → Study Day = Missing Ref Date < Baseline Visit Date → Study Day = Ref Date – Baseline Visit Date Ref Date ≥ Baseline Visit Date → Study Day = Ref Date – Baseline Visit Date + 1

9.4.2. Study Population

Demographics
Age

 GSK standard IDSL algorithms will be used for calculating age where birth date will be imputed as follows: 
 Any subject with a missing day will have this imputed as day '15'. Any subject with a missing date and month will have this imputed as '30th June'. Birth date will be presented in listings as 'YYYY'.

Adverse Event
For this non-drug study, an AE is any untoward medical occurrence in a clinical investigation subject which, in the opinion of the investigator, is related to a protocol-mandated procedure or one of the devices used by the subject during the study.

9.4.3. Exploratory

ALSFRS-R Total Score

The ALS functional rating scale – revised (ALSFRS-R) assesses the functioning of ALS subjects across 4 domains: gross motor activity, fine motor activity, bulbar and respiratory function. The ALSFRS-R [Cedarbaum, 1999] consists of 12 questions each of which are scored on a 5-point scale from 0-4, where 4 is the best possible outcome and 0 is the worst.
 
The total score will be calculated by summing responses to each of the 12 individual questions. The maximum total score is therefore 48, lower scores indicate worse functioning. If there are any missing questions, then the total score will be set to missing.
 
ALSFRS will be grouped to four different domains: Fine motor, Gross motor, Respiratory and Bulbar Domain [Cedarbaum, 1999]

FVC

FVC is a measure of respiratory function and is the volume of air that can forcibly be blown out after a single, full breath. FVC is a sensitive measure of ALS disease progression, is used as a standard test for ALS management, and is recommended as a secondary outcome measure in ALS clinical trials [Cudkowicz, 2004; Czaplinski, 2006; Clavelou, 2013].
 
FVC will be performed by experienced site personnel according to local protocol using a calibrated spirometer. Every effort should be made to have the same individual perform the FVC for a given subject throughout the study. For each time point, the best FVC result (in litres) will be recorded in the eCRF.

Relative Rate of Decline and Monthly Rate of Decline (Slope)

Relative Rate of Decline = $\frac{\text{Value at a time point} - \text{Value at the Baseline}}{\text{Value at the Baseline}}$
 
 $\frac{\text{Monthly rate of decline at each visit} = \frac{\text{Change from baseline of the endpoint at each post-baseline visit}}{\text{Study day}/30.4}}$ 
 
Monthly Rate of Decline= Average of Monthly Rate of Decline at each visit and is populated only for the last visit.
 
For Monthly Rate of Decline, if an assessment took place over a number of consecutive days then the average of that will be taken and the recent visit (last time point) will be considered to calculate study day.

Actigraphy

Activity classifiers = Active / lying / “sedentary not lying”.
 
NMTMSG – expected to be 24 hr (1440 mins) but could be less if partial recording day NMTMSG = Active, lying, “sedentary not lying”, off
 
Each activity classifier & activity endpoint is recorded by McLaren TWICE, once for day time once for night time.
 
1440 = day time Active, day time lying, day time “sedentary not lying”, day time off + night time Active, night time lying, night time “sedentary not lying”, night time off
 
Therefore, wear time = 1440 minus [day off time + night off time]
 
Off time here represents the time that the sensor was either switched off or the patient was not wearing it (or both).
 
For all the parameters, derivation will be done twice – one with all data and one with the quality data (i.e., excluding data quality deviators).

For each endpoint for the CSR (& interpretation of the study) 3 splits of data will be reported:

- Day time activity endpoints – from McLaren
- Night time activity endpoints – from McLaren
- 24 hour endpoints – derived by GSK – add day time + night time values

DERIVED	Wear time (mins)	Time Active + Time sedentary [where time sedentary = time lying + time sedentary not lying]
DERIVED	Duration of day time wear time (mins)	Day time wear time = day time Active + day time lying + day time “sedentary not lying”
DERIVED	Duration of night time wear time (mins)	Night time wear time = night time Active + night time lying + night time “sedentary not lying”
ACTIVETM	Overall time spent active Average day time active % daytime ACTIVE % night time ACTIVE	Number mins per day/night for 24-hour recording period Add up the total amount of time active across all the recording periods and divide by the number of recording periods. 1 value per subject per time point DAYTIME ACTIVETM (Day 1+2+3) divided by total amount of day time duration across the 3 recording days – expressed as a % Where total amount of daytime duration = [Day 1-day time ACTIVETM + day time LIETM + day time “sedentary not lying” – SEDTMNL] + Day 2 (ditto) + Day 3 [ditto] NIGHTTIME ACTIVETM (Day

		
1+2+3) divide by total amount of night time duration across the 3 recording days – expressed as a %
 
Where total amount of night time duration = [Day 1-night time ACTIVETM + night time LIETM + night time “sedentary not lying” – SEDTMNL] + Day 2 (ditto) + Day 3 [ditto]

SEDTMNL	
Overall time spent sedentary not lying
 
% daytime SEDENTARY NOT LYING
 
% night time SEDENTARY NOT LYING
	Needs the same approach as above
LIETM	
Overall time spent lying
 
% daytime LYING
 
% night time LYING
	Needs the same approach as above
SEDTM	
Over all time spent sedentary
 
% daytime SEDENTARY
 
% night time SEDENTARY
	Same Approach as above
OFFTM	Time spent with sensor	
ACTIVISC	
Total activity score
 
24- Hour
 
Daytime total activity score
 
Night time total activity score
	
Total Activity Score (add day + night)
 
Day time total activity score (Day 1+2+3) divide by the total day time for that protocol time point.
 
Night time total activity score Day (Day 1+2+3) divide by the total day time for that protocol time point.

MAXACTSC	The maximum score from a 1 min window in a 24-hour	3 values per protocol time point or more if more days are

	
period
 
Daytime maximum activity score
 
Daytime mean maximum activity score (mean of all recording periods)
 
Night time maximum activity score
 
Night time mean maximum activity score (mean of all recording)
	
recorded for home monitoring.
 
 • Take the maximum over the 3 days • Average over 3 days
WKPER01, WKPER02, WKPER05, WKPER15, WKPER30	Active Periods (Numbers)	To normalise 'Active Periods (Number)' to a per hour unit (Algorithm is given below)
WKPERDUR	Average duration of active periods greater than 1 minute.	

To normalise 'Active Periods (Number)' :

1. Add up the total number of 'active periods' for the recording periods (value 1).
 - Please note this is done by adding the 'number of active periods (all the categories) 1min<x<2min' + 'number of active periods 2min<x<5min' + 'number of active periods 5min<x<15min' + 'number of active periods 15min<x<30min' + 'number of active periods >30min'
2. Calculate the 'wear time' for the recording period in days(i.e. minutes/ 1440). (value 2).
 - Please remember that 'wear time = active + sedentary time' for the recording period (either day time or night time)
3. Value 1 / Value 2 is the normalised measure required

Rules for reconciliation of Actigraphy and Diary data

Actigraphy and Diary data will be reconciled and a frequency table on the rules below will be summarized;

Rule1: Subjects present both in Actigraphy and Diary data

Rule2: Subjects present only in Actigraphy data

Rule3: Subjects present only in Diary data

Night Time Endpoints	
These endpoints need to be reported as the “average” or “mean” for each protocol time point (due to the amount of day or night time not matching a protocol day or night)	
CODE	DESCRIPTION
NNTMTEPHR	Number Night Time Movement Episodes/Hr
NRESTEF	Percent Time Night-time Rest Efficiency
RFRGI	Rest Frag Index=Move Time/Num Movement Episode
AVGDURMTE	Average Duration Movement Episodes
Number Night Time Movement Episodes/Hr. NNTMTEPHR	
Limitations of each 24-hour recording period = the 24-hour recording periods do NOT match protocol days, due to the mixed start times that are governed by the sensor “activation.” (first data recorded by the sensor) – as such reporting the data out by recording day does NOT make sense, the data must be reported over the 3 days for each protocol timepoint (ie data need to be averaged out). A note pertaining to this must be added to any data that lists out the raw data for each recording period.
 
Average number night time movements/hour (Day 1+2+3) divide by 3, ie Day 1 + Day 2 etc. / actual number of recording periods at each time point (sometimes there are more or less values at each protocol time point)

Percent Time Night-time Rest Efficiency NRESTEF	
Core study phase only. Limitations as above
 
Average % time night time rest efficiency (Day 1+2+3 values) divide by 3, ie Day 1 value + Day 2 value etc. / actual number of recording periods at each time point (sometimes there are more or less values at each protocol time point)

Rest Frag Ind=Move Time/Num RFRGI Movement Episode	
Core study phase only. Limitations as above
 
Average night time rest fragmentation index (Day 1+2+3 values) divide by 3, ie Day 1 value + Day 2 value etc. / actual number of recording periods at each time point (sometimes there are more or less values at each protocol time point)

Avg Duration Movement Episodes AVGDURMTE
	
Done for each 24 hours' period But again, need 1 value for protocol time point. An average of the average over 3 days. – Use the number of active periods in the categories above – add up to derive a total, use that total to create a more accurate average.
 
Average duration of movement disorders = values [Day 1 + day 2 + day 3]/total number of night time movements [Days 1+2+3]

---	--

Speech Assessments

The 4 tests for speech assessments are:

- Short ah
 - Central tendency of fundamental F0, relative jitter, relative shimmer
- Long ah
 - Central tendency of fundamental F0, relative jitter, relative shimmer
- Single word – doily
 - Average phoneme rate, average phonation time
- Running speech (bamboo passage)
 - Speaking rate % pause time

CODE	DESCRIPTION
AA001	Central tendency of fundamental F0 (code 001: short ah) HZ (code 002: long ah) ?? middle five seconds of the phonation interval??
AA002	Relative Jitter (code 001: short ah) % (code 002: long ah)
AA003	Relative Shimmer (code 001: short ah)

%	(code 002: long ah)
AA004 (Hz/s)	Average phoneme rate (Phoneme – subpart of word) code 003: “single word” doily
AA005 (s)	Average phonation time code 003: “single word” doily
AA007 %	% pause time (Code 004: running speech)
AA008 (WPM)	Speaking rate (Code 004: running speech)

Heart Rate Variability (all LF/HF HRV metrics are over 5 minutes’ windows)

HRV data are captured for each of the activity classifiers: Active + Lying + “sedentary not lying”. “Lying minus active” and “Lying minus sedentary not lying” is derived based on the following:

MLFHFN	Mean LF/HF (Avg over 5 min windows of lying down)	Use the sum of the means over each recording day (Day 1 + Day 2 + Day 3) divided by the total number of recording points over the 3 days (number Day 1+2+3) (number of lying periods of good enough quality to obtain HRV from)
VLFHFN	Var of LF/HF (Avg over 5 min windows of lying down)	Use the sum of the variances over each recording day (Day 1 + Day 2 + Day 3) divided by the total number of recording points over the 3 days (number Day 1+2+3) (number of lying periods of good

		enough quality to obtain HRV from)
MLFHFSD	Mean LF/HF (avg-stationary-day) Stationary = sedentary not lying	Derive 1 average value for each protocol time point, Use the sum of the means over each recording day (Day 1 + Day 2 + Day 3) divided by the total number of recording points over the 3 days (number Day 1+2+3) (number of 'sedentary not lying' periods of good enough quality to obtain HRV from)
VLHFSD	Var of LF/HF (avg-stationary-day) Stationary = sedentary not lying	Derive 1 average value for each protocol time point, Use the sum of the variances over each recording day divided by the total number of recording points (number of 'sedentary not lying' periods of good enough quality to obtain HRV from)
MLHFAD	Mean LF/HF (avg-daytime activity)	Derive 1 average value for each protocol time point, Use the sum of the means over each recording day divided by the total number of recording points (number of active periods of good enough quality to obtain HRV from)
VLHFAD	Var of LF/HF (avg-daytime activity)	Derive 1 average value for each protocol time point, Use the sum of the variances over each recording day divided by the total number of recording points (number of active periods of good enough quality to obtain HRV from)
MRMSSD	Mean RMSSD (24 hr avg)	
VRMSSD	Var of RMSSD (24 hrs avg)	

- HRV effect of being upright = LF/HF stationary minus LF/HF lying
- HRV effect of activity = LF/HF active (MLHFAD) minus LF/HF lying (MLHFN)

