4. ANALYSIS POPULATIONS

Population	Definition / Criteria	Analyses Evaluated
Enrolled	
 Comprise of all subjects who have signed consent and are not a screen failure 	
 Study population
Full Analysis Set (FAS)	
 This will consist of all subjects with at least one post baseline measure for the ALSFRS-R and at least one physical activity/movement measure. 	
 Study Population Exploratory
Safety	
 Comprise of all subjects who carried out at least one protocol specified procedure. 	
 Safety
Screen Failure	
 Comprise of all subjects who were a screen failure 	
 Study Population

NOTES:

- Please refer to [Appendix 11](#): List of Data Displays which details the population to be used for each displays being generated.

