7.1.2. Planned Statistical Exploratory Analyses

Statistical Analyses
Endpoint(s)

 • Movement/physical activity (Actigraphy) endpoints as measured by the accelerometer device. See Section 2.2 for details. • Heart rate variability endpoints as measured by the electrode device. See Section 2.2 for details. • Speech endpoints. See Section 2.2 for details. • ALSFRS-R total score and ALSFRS-R scores for 4 domains: gross motor activity, fine motor activity, bulbar and respiratory function • FVC
Model Specification

 • Descriptive Statistics 
 ○ Actigraphy 
 ▪ The absolute, change from baseline, and the relative rate of decline for Actigraphy related endpoints will be summarized for each protocol time point using the FAS population ▪ The monthly rate of decline for the whole study period for Actigraphy related endpoints will be summarized using the FAS population ▪ The absolute values over time and relative rate of decline of Actigraphy related endpoints along with the total score over time and relative rate of decline of ALSFRS-R will be plotted against time (X), respectively. ○ Heart Rate Variability 
 ▪ The absolute values, change from baseline, and the relative rate of decline for HRV related endpoints (Mean & Variance for the LF/HF and 24 hours RMSSD analyses) will be summarized for each protocol time point using the FAS population ▪ The monthly rate of decline for the whole study period for HRV related endpoints (Mean & Variance for the LF/HF and 24 hours RMSSD analyses) will be summarized using the FAS population ▪ The absolute values and relative rate of decline of HRV related endpoints (Mean & Variance for the LF/HF and 24 hours RMSSD analyses) along with the absolute and relative rate of decline of ALSFRS-R will be plotted against time (X) respectively. ▪ The Average Value and the raw data of the endpoints from McLaren will be listed ○ Speech assessment

Statistical Analyses

- The absolute values, change from baseline, and the relative rate of decline for Speech related endpoints will be summarized for each protocol time point using the FAS population
- The monthly rate of decline for the whole study period for Speech related endpoints will be summarized using the FAS population

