9.5. Appendix 5: Premature Withdrawals & Handling of Missing Data

9.5.1. Premature Withdrawals

Element	Reporting Detail
General	
 • Subject study completion (i.e. as specified in the protocol) was defined as a subject is one who has completed the study through the Week 48 visit. • All available data from subjects who were withdrawn from the study will be listed and all available planned data will be included in summary tables and figures, unless otherwise specified.

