9.7. Appendix 7: Examination of Covariates, Subgroups & Other Strata

9.7.1. Handling of Covariates, Subgroups & Other Strata

There was no randomisation and therefore no strata used in this study.

Due to the small number of subjects in the study, no subgroups will be specified here although subgroup analyses may take place ad hoc.

The following is a list of covariates that may be used in descriptive summaries and/ or statistical analyses (See Section 7.1.1 and Section 7.1.2 for further details).

Additional covariates of clinical interest may also be considered.

These analyses will be carried out as part of ADHOC if necessary.

Category	Covariates and / or Subgroups
Correlation of ALSFRS-R and movement actigraphy data/ HRV data	In additional to the model described in Section 7.1.2, the following explanatory variables may be considered: 
 • Baseline value for each of the dependent variables being correlated • Phenotype at onset: Bulbar/Limb/Other • Age at baseline • Sex – Male/ Female • Time since onset of muscle weakness
Correlation of FVC/ ALSFRS-R and speech data	In additional to the model described in Section 7.1.2, the following explanatory variables may be considered: 
 • Baseline value for each of the dependent variables being correlated • Phenotype at onset: Bulbar/Limb/Other • Smoking status at baseline • Age at baseline • Sex – Male/ Female • Time since onset of muscle weakness
Mixed model repeated measures analyses	For the MMRM Baseline, Visit, Baseline by Visit covariates will be included in model. The following explanatory variables may also be considered: 
 • Phenotype at onset: Bulbar or Other/ Limb • Smoking status at baseline • Age at baseline • Sex – Male/ Female • Time since onset of muscle weakness

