9.8. Appendix 8: Multiple Comparisons & Multiplicity

As this is an exploratory study, no adjustment will be made for multiple comparisons. Assessments about the correlation between endpoints will be made on the strength of the correlation coefficients.

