2.55.	FAS	EFF_T1	Summary of Monthly Rate of Decline of Maximum Score (1 min – 24 Hour Window) (Quality data)	Same as above	SAC
2.56.	FAS	EFF_T1	Summary of Active Periods (Numbers) (All data)	For day and night active periods separately & for each category (> 1 to <= 2 minutes, > 2 to <= 5 minutes etc. etc): Categorise into Day and Night Time Modify EFF_T1 as: Add n (%) instead of statistics Add columns for categories	SAC
2.57.	FAS	EFF_T1	Summary of Active Periods (Numbers) (Quality data)	Same as Above	SAC

Efficacy: Tables					
No.	Population	IDSL / TST ID / Example Shell	Title	Programming Notes	Deliverable [Priority]
2.58.	FAS	EFF_T1	Summary of Active Periods (Duration) (All data)	Categorise into Day and Night Time	SAC
2.59.	FAS	EFF_T1	Summary of Active Periods (Duration) (Quality data)	Same as Above	SAC
2.60.	FAS	EFF_T1	Summary of Change from Baseline of Active Periods (Duration) (All Data)	Same as Above	SAC
2.61.	FAS	EFF_T1	Summary of Active Change from Baseline of Periods (Duration) (Quality data)	Same as Above	SAC
2.62.	FAS	EFF_T1	Summary of Relative Rate of Decline of Active Periods (Duration) (All data)	Same as Above	SAC
2.63.	FAS	EFF_T1	Summary of Relative Rate of Decline of Active Periods (Duration) (Quality data)	Same as Above	SAC
2.64.	FAS	EFF_T1	Summary of Monthly Rate of Decline of Active Periods (Duration) (Quality data)	Same as Above	SAC
2.65.	FAS	EFF_T3	Statistical Analysis of Relationship between Absolute Values of Actigraphy endpoints and Absolute Value of Total ALSFRS-R		SAC
2.66.	FAS	EFF_T3	Statistical Analysis of Relationship between Change from Baseline of Actigraphy endpoints and Change from Baseline of Total ALSFRS-R		SAC
2.67.	FAS	EFF_T3	Statistical Analysis of Relationship between Slope of Actigraphy endpoints and Slope of Total ALSFRS-R		SAC

Efficacy: Tables					
No.	Population	IDSL / TST ID / Example Shell	Title	Programming Notes	Deliverable [Priority]
2.68.	FAS	EFF_T3	Statistical Analysis of Relationship between Absolute Values of Actigraphy endpoints and Absolute Value of gross motor domain of ALSFRS-R		SAC
2.69.	FAS	EFF_T3	Statistical Analysis of Relationship between Change from Baseline of Actigraphy endpoints and Change from Baseline of gross motor domain of ALSFRS-R		SAC
2.70.	FAS	EFF_T3	Statistical Analysis of Relationship between Slope of Actigraphy endpoints and Slope of gross motor domain of ALSFRS-R		SAC

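### The monthly rate (Slope) averages per-visit rates with equal weight, which makes it a needlessly noisy slope and distorts the slope-slope correlations by an amount the SAP does not let one fix

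*SAP*

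**What the plan says.** Section 9.4.3 computes, at each post-baseline visit, the change from baseline divided by study day/30.4. The subject's monthly rate, which the heading also calls the slope, is the "Average of Monthly Rate of Decline at each visit and is populated only for the last visit". No time weighting or regression is specified.

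The time-and-events table (Section 9.1.1) schedules ALSFRS-R in clinic at Weeks 0, 12, 24, 36 and 48 and "by telephone at Weeks 4, 8, 16, 20, 28, 32, 40, and 44", which gives 12 post-baseline points. Home actigraphy and HRV follow the same 4-weekly rhythm. Speech and FVC are taken at clinic visits only, which gives four post-baseline points.

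Section 7.1.2 uses the rate descriptively: "The monthly rate of decline for the whole study period for Actigraphy related endpoints will be summarized using the FAS population", and likewise for HRV and speech. Section 9.11.4 adds correlation tables, for example "Statistical Analysis of Relationship between Slope of Actigraphy endpoints and Slope of Total ALSFRS-R" (Table 2.67). The FAS takes in "all subjects with at least one post baseline measure for the ALSFRS-R" (with at least one activity measure), and for withdrawn subjects "all available planned data will be included in summary tables and figures". Section 9.8 states: "Assessments about the correlation between endpoints will be made on the strength of the correlation coefficients".

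**The concern.** A rate taken over four weeks is a much noisier estimate of monthly decline than one taken over 48 weeks, yet the two count equally. Under independent errors the Week 4 rate has (48/4)² = 144 times the variance of the Week 48 rate. The same baseline error also sits in every rate and does not average out.

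The result feeds eight correlation tables (2.67, 2.70, 2.73, 2.104, 2.131, 2.132, 2.139, 2.142), eight scatter plots (Figures 2.39, 2.42, 2.45, 2.64, 2.81, 2.82, 2.87, 2.90) and 19 monthly-rate summary tables. Endpoints are judged by the size of the coefficient, and Section 9.7.1 rules out prespecified subgroups "Due to the small number of subjects in the study". Avoidable slope error could therefore change how a digital endpoint looks as a progression marker.

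**Working it through.** The SAP states no variance, error correlation or sample size for the slope, so there is no figure of its own to reproduce.

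**Inputs.** Weeks 0, 4, …, 48 and Weeks 0, 12, …, 48 (Section 9.1.1), with t = weeks × 7/30.4 months. Error structures are assumed: independent, AR(1) with 0.3, 0.6 or 0.8 per 4 weeks, and random walk.

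**Weights.** With k post-baseline visits, the SAP rule gives visit j the weight 1/(k·t_j) and baseline the weight −mean(1/t). Least squares gives each point (t − t̄)/Σ(t − t̄)². Error variance is w′Cw, where C is the error correlation matrix.

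**Independent errors, to Week 48, in units of the visit error variance.**
- 4-weekly, SAP rule: mean(1/t) = 0.2808, so baseline contributes 0.2808² = 0.0788 and the later visits 0.0128. The total is 0.0916, of which baseline is 86%.
- 4-weekly, least squares: 1/154.4 = 0.0065. Ratio 14.1.
- 12-weekly, SAP rule: 0.1885² + 0.0117 = 0.0472 (baseline 75%). Least squares: 1/76.35 = 0.0131. Ratio 3.6.

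**Error-variance ratio, SAP rule to least squares.**

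| Schedule, last visit | Indep. | AR 0.3 | AR 0.6 | AR 0.8 | Random walk |
|---|---|---|---|---|---|
| 4-weekly, Week 48 | 14.1 | 7.8 | 3.9 | 2.4 | 1.55 |
| 4-weekly, Week 24 | 5.8 | 3.7 | 2.4 | 1.8 | 1.5 |
| 4-weekly, Week 12 | 2.6 | 2.0 | 1.65 | 1.5 | 1.4 |
| 4-weekly, Week 4 | 1.0 | 1.0 | 1.0 | 1.0 | 1.0 |
| 12-weekly, Week 48 | 3.6 | 3.5 | 2.8 | 2.0 | 1.4 |
| 12-weekly, Week 24 | 1.75 | 1.7 | 1.6 | 1.4 | 1.25 |

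Using the SAP's study day, which adds one day, changes little: 14.1 becomes 13.6 and 3.60 becomes 3.54. Against a line forced through the baseline value, Σt(Y − Y₀)/Σt², the completer ratios are 1.5 to 4.9 (4-weekly) and 1.35 to 2.5 (12-weekly). If only baseline, Week 44 and Week 48 survive, the ratio to least squares is about 1.01.

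**Effect on a correlation.** Assume an ordinary correlation of slopes across subjects, a true slope correlation ρ, the same visit noise in both measures (SD equal to n between-subject SDs of the monthly slope), and a visit-error correlation e between the two measures. With a common schedule and error variance V as above, the expected value is approximately (ρ + e·n²V)/(1 + n²V).

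Completers, 4-weekly, errors independent over time:
- ρ = 0.70, e = 0, n = 2: SAP rule 0.70/(1 + 4 × 0.0916) = 0.51; least squares 0.70/(1 + 4 × 0.0065) = 0.68.
- Same with n = 0.5, 1, 4: 0.68, 0.64, 0.28 against 0.70, 0.70, 0.63.
- ρ = 0.70, e = 0.9, n = 2: SAP rule (0.70 + 0.9 × 0.366)/1.366 = 0.75, above the truth.
- ρ = 0, e = 0.5, n = 2: SAP rule 0.13; least squares 0.01.

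With AR(1) 0.8, e = 0 and n = 2, the SAP rule gives 0.60 and least squares 0.65. For speech (12-weekly) against ALSFRS-R (4-weekly) as in Table 2.139, independent errors and e = 0, n = 1 and 2 give 0.65 and 0.55 against 0.69 and 0.67.

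**Early leavers.** Assume 70% followed to Week 48, 10% to Week 24, 10% to Week 12, 5% to Week 8 and 5% to Week 4, with withdrawal unrelated to slope, independent errors and e = 0. Mean V is 0.320 (SAP rule) and 0.180 (least squares). At n = 2 the correlation is 0.70/(1 + 4 × 0.320) = 0.31 against 0.70/(1 + 4 × 0.180) = 0.41. The 5% who leave at Week 4 supply 66% of the least-squares error variance, so per-subject least squares recovers only part of the loss.

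**The case against.** The rule is fully defined and contradicts nothing, so this is a choice between estimators in an exploratory study. Slope correlations appear only in the display list. The analyses that Section 7.1.2 describes, and that the synopsis uses to decide on further work, are the absolute and change-from-baseline correlations. The factor of 14 needs independent errors, all visits to Week 48 and a least-squares line with a free intercept; quality exclusions will remove some actigraphy points. At low noise the loss is about 0.02 in the coefficient, and actigraphy values already pool about three recording days. All of this stands and limits the weight of the point.

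A reader might infer that the rule always makes an endpoint look less related to ALSFRS-R or FVC than it is. The documents do not support that. Attenuation follows only if visit errors in the two measures are unrelated, and because they are assessed around the same visits, shared error cannot be excluded. A reader might also infer that the 19 monthly-rate summaries are biased. Under linear decline the average of the rates is unbiased apart from the added study day (under 1%), so only their spread and standard errors are inflated.

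What survives is the loss of precision. In the error structures tried, the SAP rule was never more precise than least squares for subjects with two or more post-baseline visits.

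**Conclusion.** The point holds as one of efficiency and distortion, at the level of a change to consider. Confidence is high for the precision ratios, given the schedule and the assumed error structure. The effect on any correlation is conditional, because the SAP gives neither the visit noise relative to the slope spread nor the correlation of errors within or between measures. It ranges from trivial at low noise, through modest with strong autocorrelation, to substantial with noisy and nearly independent visits, and it can go in either direction. The absolute and change-from-baseline correlations are unaffected.

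**What to change.** In Section 9.4.3, define the monthly rate per subject as the least-squares slope of all observed values, baseline included, on elapsed months. Use it in the slope tables, scatter plots and monthly-rate summaries, and report how many subjects have fewer than three time points.

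Optionally, for the slope correlations, estimate the random-slope correlation from a joint bivariate model of the endpoint and ALSFRS-R (or FVC), allowing residuals to correlate between the two measures, with per-subject least squares as the fallback. Such a model down-weights short follow-up without excluding it.

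The cost is a change of wording plus a per-subject regression, or one mixed model per endpoint pair, on data already collected. The drawbacks are that linear decline is assumed, that least squares gains little for early leavers (nothing with a single post-baseline visit), and that the joint model may not converge for every pair in a small study.
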